5.4.4 Treatment modification for MT-3724 and LEN due to neutropenia or thrombocytopenia

This guidance is applicable to any neutropenia and/or thrombocytopenia that, in the investigator's opinion, is at least possibly related to any of the study drugs.

If treatment modification of MT-3724 or LEN is warranted due to neutropenia or thrombocytopenia, and the continuation of treatment is appropriate at investigator's discretion after consultation with the medical monitor, then the dose of MT-3724 or LEN will be adjusted as described in Table 6.

Table 6: Dose Adjustments of MT-3724 or LEN in Response to Neutrophil and Platelet Nadir Counts

Absolute neutrophil nadir count		Platelet nadir count	MT-3724 and/or LEN dose modification ¹
>500/ μ l or <500/ μ l for <5 days	and	\geq 25,000/ μ l	No change
<500/ μ l for \geq 5 days	and/or	<25,000 for \geq 7 days with or without active bleeding, OR <50,000/ μ l for \geq 7 days with clinically significant bleeding ²	Decrease by \geq 25% or according to reference prescribing information
Febrile neutropenia ³	and/or	<25,000/ μ l for \geq 7 days with or without active bleeding, OR <50,000/ μ l for \geq 7 days with clinically significant bleeding ²	Decrease by \geq 25% or according to reference prescribing information

LEN = lenalidomide

¹MT-3724 dose reduction translates to a reduction by \geq 25%, and LEN dose reduction by 1 level translates to a reduction by \geq 5 mg once daily; the actual amounts for either agent will be determined by the investigator after consultation with the medical monitor.

²Clinically significant bleeding is that which requires platelet transfusion.

³Febrile neutropenia is defined as absolute neutrophil count <1000/ μ l and fever (a single body temperature reading of $>38.3^{\circ}\text{C}$ [101°F] or a sustained body temperature of $\geq38.0^{\circ}\text{C}$ [100.4°F] for more than one hour).

Repeated dose reductions are permitted if continued treatment is supported by the investigator's assessment of the benefit-risk ratio, but not below 5 μ g/kg/dose for MT-3724.

5.4.5 Treatment modification for MT-3724 and LEN due to increased AST, ALT and/or bilirubin levels

This guidance is applicable to increased serum AST, ALT and/or bilirubin levels that, in the investigator's opinion, is at least possibly related to any of the study drugs.

If treatment modification of MT-3724 or LEN is warranted due to increased AST, ALT and/or bilirubin levels, and the continuation of treatment is appropriate at investigator's

discretion after consultation with the medical monitor, then the dose of MT-3724 or LEN will be adjusted as described in Table 7.

Table 7 Dose Adjustments in Response to the Worst Increase in Aspartate Aminotransferase, Alanine Aminotransferase, or Bilirubin

Worst AST and/or ALT increase		Worst bilirubin increase	MT-3724 and/or LEN dose modification
$\leq 5 \times \text{ULN}$ (isolated)	or	$\leq 1.5 \times \text{ULN}$ (isolated)	
 No change in study drug Monitor subject
$>5 \times \text{ULN} - 8.0 \times \text{ULN}$ (for subjects enrolled with AST/ALT $<3 \times \text{ULN}$)	and/or	$>1.5 \times \text{ULN} - 5.0 \times \text{ULN}$	
 Temporarily or permanently (see next row) discontinue study drug Monitor subject Continue at dose reduced by 1 dose level after abnormal values resolve to Grade ≤ 1 or baseline¹
AST or ALT $>8.0 \times \text{ULN}$ for any period of time (for any subject) or AST or ALT $>5 \times \text{ULN}$ for more than 2 weeks (for subjects enrolled with AST/ALT 3-5 $\times \text{ULN}$)			
 Permanently discontinue study drug
$>3.0 \times \text{ULN}$ (without findings of cholestasis defined as serum alkaline phosphatase $<2 \times \text{ULN}$)	and	$> 2.0 \times \text{ULN}$ or INR >1.5	
 Permanently discontinue study drug
$>3.0 \times \text{ULN}$ with the appearance of fatigue, nausea, vomiting, right upper quadrant pain or tenderness, fever, rash, and/or eosinophilia ($>5\%$)			
 Permanently discontinue study drug
		$>5.0 \times \text{ULN}$	
 Permanently discontinue study drug

ALT = alanine aminotransferase; AST = aspartate aminotransferase; LEN = lenalidomide; ULN = upper limit normal

These are recommendations in situations where a possible relatedness of liver enzyme elevations to study drug is assumed. Further these being recommendations that cannot consider all clinical circumstances, the investigator is encouraged to contact the medical monitor to discuss alternative course of action.

¹MT-3724 dose reduction by 1 dose level translates to an approximate reduction by $\geq 25\%-33\%$, and LEN dose reduction translates to a reduction by ≥ 5 mg once daily; the actual amounts for either agent will be determined by the investigator after consultation with the medical monitor.

Repeated dose reductions are permitted if continued treatment is supported by the investigator's assessment of the benefit-risk ratio, but not below 5 $\mu\text{g}/\text{kg}/\text{dose}$ for MT-3724.

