5.4.1 MT-3724 treatment modification

Any of the following TEAEs in any treatment cycle may trigger MT-3724 treatment modification, if deemed at least possibly related to MT-3724 by the investigator after consultation with the medical monitor.

- Any TEAE irrespective of the time of onset, that would otherwise fulfill the DLT criteria ([Appendix 4](#))
- Grade ≥ 2 IRR, or another Grade ≥ 2 hypersensitivity reaction
- Any other toxicity related to MT-3724, irrespective of the type or severity or time of onset, that warrants dose modification in the opinion of the investigator after consultation with the medical monitor. This may be Grade 1 or Grade 2 toxicity that notably limits the

activities of daily life (e.g. long-lasting fatigue or anorexia), making a dose reduction necessary to ensure the subject's compliance.

The following actions are recommended after any of the above TEAEs occur.

- The investigator should notify the medical monitor about the TEAE within 24 hours of the awareness.
- The investigator should monitor the subject and if necessary, perform diagnostic procedures and therapeutic interventions.
- If a subject experiences a TEAE in cycle 1 that is related to MT-3724 and qualifies as a DLT, then the MT-3724 treatment should be discontinued, except if continued treatment is supported by the investigator's assessment of the benefit-risk ratio. In this case, the MT-3724 re-treatment should be delayed until the TEAE resolves to Grade ≤ 1 . Further, the MT-3724 re-treatment should start at a $\geq 25\%$ reduced MT-3724 dose.
- If a subject experienced a Grade ≥ 2 IRR, or another Grade ≥ 2 hypersensitivity event, Grade ≥ 2 CRS or Grade ≥ 2 CLS, the investigator should obtain serum samples for cytokines, complement and histamine as soon as possible after the TEAE onset. These samples should be marked "STAT" and shipped immediately to the laboratory.
- MT-3724 dose may be **reduced** by $\geq 25\%$ at the investigator's discretion after consultation with the medical monitor. The number of dose reductions per subject is not limited, except that the reduced dose cannot be $< 5 \mu\text{g}/\text{kg}/\text{dose}$ (this was the lowest dose tested in the clinic so far).
- No intra-subject escalation of MT-3724 dose is permitted after previous MT-3724 dose reduction.

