APPENDIX 4. DLT CRITERIA

GENERAL PRINCIPLES

A TEAE will be declared as DLT if both of the following criteria are met:

1. The TEAE occurred after the start of infusion in cycle 1 of Part 1.
 - a. If a TEAE that fulfills a DLT criterion is observed in cycle ≥ 2 of Part 1, then the sponsor may declare this event a DLT after consultation with the investigator(s).
2. The TEAE is at least possibly related to MT-3724, as determined by the sponsor after consultation with the investigator(s).

Note: TEAEs related to LEN will not be declared a DLT unless they exceed in severity the worst grade described or are not mentioned in the reference prescribing information. If a Grade ≥ 3 TEAE related to LEN is more severe than the worst grade described in the reference prescribing information or has not been reported in the reference prescribing information, then the sponsor may declare this event a DLT after consultation with the investigator(s).

The severity of TEAEs potentially fulfilling the DLT criteria will be graded according to the CTCAE v.5.0.

POTENTIALLY QUALIFYING TEAEs: Any TEAE listed below may represent a DLT for MT-3724 in this study.

Hematological TEAEs

- Grade ≥ 3 febrile neutropenia (ANC $<1000/\mu\text{l}$ and a single body temperature reading of $>38.3^\circ\text{C}$ (101°F) or a sustained body temperature of $\geq 38.0^\circ\text{C}$ (100.4°F) for more than 1 hour)
- Grade 4 neutropenia (ANC $<500/\mu\text{l}$) for >5 days; if the investigator determines that G-CSF therapy for Grade 4 neutropenia is essential within ≤ 5 days of onset, then this AE will also qualify as DLT
- Grade 3 thrombocytopenia ($<50,000/\mu\text{l}$ and $\geq 25,000/\mu\text{l}$) with clinically significant bleeding (i.e., bleeding requiring platelet transfusion)
- Grade 4 thrombocytopenia ($<25,000/\mu\text{l}$) with or without bleeding
- Grade 4 anemia

Nonhematological TEAEs

- Grade ≥ 2 Cytokine Release Syndrome
- Grade ≥ 3 Capillary Leak Syndrome
- Grade ≥ 3 acute kidney injury
- AST and/or ALT increase >5.0 times ULN (>8.0 times for those with liver involvement)
- AST and/or ALT increase >3.0 times ULN with concomitant increase in total bilirubin ≥ 2.5 times ULN
- Total bilirubin >4.0 times ULN

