Note: for AST, ALT and bilirubin the investigator in consultation with the Medical Monitor and the sponsor should diligently assess if the value above either 5.0, 3.0 or 1.5 x ULN (depending on laboratory values as specified above), could be interpreted as non-DLT in light of the elevated baseline value (see CTCAE v5.0) and liver involvement.

- Grade ≥ 3 infusion-related reaction or other Grade ≥ 3 hypersensitivity reaction
- Any Grade ≥ 3 electrolyte abnormality that does not resolve, with or without intervention, to Grade <2 within 72 hours.
- Any other Grade ≥ 3 nonhematological toxicity **excluding** the following:
 - Nausea, vomiting, or diarrhea, if manageable with antiemetic or antidiarrheal agents within 7 days of onset
 - Fatigue lasting ≤ 72 hours
 - Grade 3 laboratory abnormalities, if asymptomatic and without a clear clinical correlate, as determined by the sponsor after consultation with investigator(s).
- Any other toxicity at least possibly related to MT-3724, irrespective of the type or severity, that would qualify as DLT, as determined by the sponsor after consultation with investigator, considering the severity, duration, poor response to remedial therapy and/or inadequate resolution. This may be Grade 1 or Grade 2 toxicity that notably limits the activities of daily life to the extent that makes dose reduction necessary to ensure subject's compliance (e.g., long-lasting fatigue or anorexia).

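### Table 6 conflicts with Appendix 4 and Section 5.4.1 on blood counts, and several Table 7 permanent-stop liver events become DLTs only through catch-all bullets, leaving their place in the dose-decision count open

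*Protocol*

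**What the plan says.** Section 5.4.4 covers neutropenia and thrombocytopenia at least possibly related to either study drug. If modification is warranted and continuing is appropriate, "then the dose of MT-3724 or LEN will be adjusted as described in Table 6". Table 6 has three rows:

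- Row 1: ANC above 500/µl (or below 500 for under 5 days) and platelets of 25,000/µl or more. Action: no change. The platelet cell has no bleeding condition.
- Row 2: ANC below 500 for 5 days or more, and/or platelets below 25,000 for 7 days or more (bleeding or not) or below 50,000 for 7 days or more with clinically significant bleeding. Action: decrease by at least 25% or follow the prescribing information.
- Row 3: febrile neutropenia (ANC below 1,000 with fever), and/or the same platelet triggers. Action: as row 2.

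Appendix 4 introduces its list with "Any TEAE listed below may represent a DLT for MT-3724 in this study". The list includes Grade 3 thrombocytopenia "with clinically significant bleeding (i.e., bleeding requiring platelet transfusion"), Grade 4 thrombocytopenia with or without bleeding, and Grade 3 or higher febrile neutropenia. Neither platelet item has a minimum duration. For a cycle-1 event attributed to MT-3724, Section 5.4.1 says that if it "qualifies as a DLT, then the MT-3724 treatment should be discontinued, except if continued treatment is supported by the investigator's assessment" (a weighing of benefit against risk). In that case re-treatment waits for Grade 1 or lower and starts at a dose at least 25% lower.

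For the liver, Table 7 (Section 5.4.5) permanently discontinues drug for, among others:

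- AST/ALT above 3.0 × ULN "without findings of cholestasis defined as serum alkaline phosphatase" below 2 × ULN, combined with bilirubin above 2.0 × ULN or INR above 1.5;
- AST/ALT above 3.0 × ULN with symptoms such as fatigue, nausea or rash.

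The named hepatic DLT limits in Appendix 4 are AST/ALT above 5.0 × ULN (8.0 with liver involvement), AST/ALT above 3.0 × ULN "with concomitant increase in total bilirubin" to at least 2.5 × ULN, and total bilirubin above 4.0 × ULN.

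**The concern.** A dose-modification table and a DLT list should lead two sites to the same action for the same patient. Here a site that works from Table 6 can read no change for an event that Appendix 4 lists as a potential DLT and for which Section 5.4.1, once a cycle-1 DLT is declared, requires discontinuation or a lower dose.

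The statistical stake is the MTD, which is part of the primary objective and sets the Part 2 dose. In a 3+3 scheme each subject's status as DLT, DLT-free or not evaluable is the data. If an event ends treatment in cycle 1 but its DLT status rests on case-by-case discretion, the count behind the MTD is not fixed in advance.

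**Working it through.** There is no stated figure to reproduce. The check runs patterns through each set of rules.

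**Blood counts** (ANC above 500/µl and no fever unless stated)

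| Pattern | Table 6 | Appendix 4 |
|---|---|---|
| Platelets 25,000 to <50,000, bleeding needing platelet transfusion, <7 days | Row 1 only: no change | Listed |
| Same, ≥7 days | Row 1: no change; row 2: decrease | Listed |
| Platelets <25,000 for <7 days | No platelet row: row 1 needs ≥25,000, rows 2 and 3 need ≥7 days | Listed, with or without bleeding |
| Febrile neutropenia, ANC >500 to <1,000, platelets ≥25,000 | Row 1: no change; row 3: decrease | Listed |

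Table 6 and Appendix 4 define clinically significant bleeding in the same way, so terminology does not explain the difference.

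**Liver** (multiples of ULN; bilirubin 1 and INR 1 unless stated; no cholestasis)

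| Pattern | Table 7 | Named hepatic DLT? |
|---|---|---|
| AST/ALT 4, bilirubin 2.2 | Permanent stop (4 > 3.0, 2.2 > 2.0) | No: 4 < 5.0, 2.2 < 2.5, 2.2 < 4.0 |
| AST/ALT 4, INR 1.6 | Permanent stop (1.6 > 1.5) | No: INR is in no hepatic bullet |
| AST/ALT 4 with listed symptoms | Permanent stop | No: 4 < 5.0 |
| AST/ALT 6 for >2 weeks, enrolled at 3–5 with liver involvement | Permanent stop | No: 6 < 8.0 |
| AST/ALT 4, bilirubin 2.6 (for contrast) | Permanent stop | Yes: 2.6 ≥ 2.5 |

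The first four can become DLTs only through the two general bullets that close Appendix 4. One covers other nonhematological toxicity of Grade 3 or higher, excluding among others asymptomatic Grade 3 laboratory findings. The other covers any related toxicity of any severity that the sponsor determines to be a DLT.

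The Appendix 4 note on liver values says the investigator "should diligently assess if the value above either 5.0, 3.0 or 1.5 x ULN" may be read as a non-DLT, and refers to limits specified above it. The bullets above give bilirubin limits of 2.5 and 4.0; none gives 1.5.

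**Route into the count.** Suppose such an event stops treatment in cycle 1 and no DLT is declared.

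- Below the minimum in Section 3.6.1 (4 of 6 or 3 of 4 MT-3724 doses, and 14 of 21 LEN doses), the subject is not evaluable and is replaced under Section 4.3.2.
- At or above that minimum, the subject is evaluable and counts as DLT-free.

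**When one such event matters** (Section 3.6 rules)

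| Recorded | If also counted | Decision |
|---|---|---|
| 0 of first 3 or 4 | 1 | Escalate becomes expand to 6 |
| 1 of first 3 or 4 | 2 | Expand becomes not tolerated |
| 0 of 6 | 1 of 6 | Unchanged |
| 1 of 6 | 2 of 6 | Escalate becomes not tolerated |
| 2 or more | 3 or more | Unchanged |

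**Scale, on assumed rates only.** P(at most 1 of 6) = (1−p)^6 + 6p(1−p)^5. With an assumed counted DLT rate of 15%, this is 0.377 + 0.399 = 0.78. If a further 5%, 10% or 15% of subjects had events that would otherwise go uncounted, counting them gives p = 0.20, 0.25 or 0.30 and probabilities of 0.66, 0.53 or 0.42. This treats six subjects as one group and ignores the earlier look at 3 or 4. None of these rates comes from the documents.

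**The case against.** Several points on the other side are sound.

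- **Table 6 is conditional.** It applies only once modification is warranted, Appendix 4 says only that a listed event may be a DLT, and a DLT needs relatedness to MT-3724. Section 1.3 names thrombocytopenia among the common LEN reactions, and LEN-related events are DLTs only if they exceed, or are absent from, the prescribing information. A site following the more specific Section 5.4.1 would not restart at full dose after a cycle-1 DLT. This limits how often the conflict would arise, but does not remove it. Section 5.4.1 itself names any event meeting the DLT criteria as a possible trigger for modification, which leads to Table 6, and nothing says which section prevails. The overlapping rows and the missing row are internal to Table 6 and do not depend on attribution to MT-3724.
- **A reader might infer that no DLT criterion captures the Table 7 stops.** The documents do not support that: the two general bullets can. Only the named hepatic limits miss them.
- **A reader might call Table 7 a contradiction of the DLT definition.** It is a mismatch. Table 7 is labelled as recommendations and covers any cycle and either drug, so it may be stricter than a DLT definition tied to MT-3724 and, by default, to cycle 1.
- **A reader might add isolated bilirubin above 4.0 to 5.0 × ULN**, a named DLT for which Table 7 allows resumption. Section 5.4.1 also allows a hold and a reduced restart, and the Table 7 row includes permanent discontinuation. What remains is small: Table 7 accepts recovery to baseline as well as to Grade 1 or lower.
- **A reader might infer that one uncounted event always changes the decision.** It does so only at the counts shown.

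The MT-3724 risks and monotherapy DLTs described in Sections 1.2.1 and 1.6 include no hepatic event, so the liver route may be rare.

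**Conclusion.** The Table 6 conflict stands on the text. Two patterns of bleeding thrombocytopenia, one of platelets below 25,000 and one of febrile neutropenia receive an action at odds with Appendix 4 and Section 5.4.1, two actions at once, or none on platelet grounds. For the cycle-1 consequence, this assumes attribution to MT-3724 and a declared DLT. It is safety-relevant and cheap to correct.

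The liver point stands in a narrower form: several permanent-stop events lie outside the named hepatic limits, and their DLT status depends on general bullets that carry an exclusion or rest on sponsor discretion. With no DLT declared, the event leaves the count or enters it as DLT-free. That bears on the MTD at some counts, most plainly at 1 of 6. Its frequency cannot be estimated from the documents. The stray 1.5 × ULN reference is editorial.

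**What to change.** Reconcile Table 6, Table 7, Sections 5.4.1 and 3.6.1 and Appendix 4 so that:

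- each blood-count or liver result maps to one non-conflicting action, with Table 6 rows that neither overlap nor leave a gap;
- the documents state consistently how a related cycle-1 permanent discontinuation is handled in the dose-decision count;
- the 1.5 × ULN reference in the Appendix 4 note is corrected.

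All thresholds, doses and DLT status are for the sponsor to decide; this point proposes none.

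The cost is text edits within an amendment, with no new assessments. The downside is that some events now left to discretion would have a fixed status.

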6.4.1 Hematology, Chemistry and Urinalysis

The hematology, chemistry (with eGFR) and urinalysis assessments will be performed at the following time points:

- At screening
- Before the MT-3724 infusion on D1, D8
- On D15 of each cycle (at any time in C1-C2 and before the MT-3724 infusion in C3 and beyond)
- At the EoT Visit

If possible, the blood for chemistry assessments should be drawn after a subject has fasted for at least 2 hours, in order to facilitate a more reliable interpretation of the serum glucose result. The compliance with this recommendation (Yes/No) will be entered in the eCRF for every chemistry assessment.

Local laboratory for chemistry and hematology should be collected to assess subject status/safety if results from central laboratory will not be available pre-dose, whenever central laboratory assessments are scheduled. See Schedule of Assessments ([Study Schema](#)) for details. These results need only be entered in the EDC if there is a clinically significant finding, related to an adverse event.

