6.4.6 Coagulation

Coagulation will be assessed at the following time points:

- At Screening
- Before MT-3724 dose on D1 of cycle 3 and each odd cycle thereafter
- At the EoT Visit

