APPENDIX 1. LABORATORY PANELS

Table 10 Laboratory Assays

Hematology (central laboratory):				
WBC ¹	hemoglobin	platelet count	hematocrit	RBC and indices ²
Chemistry (central laboratory):				
albumin	amylase	lipase	creatinine	ALT
AST	CPK	calcium	chloride	GGT
LDH	serum glucose ³	magnesium	phosphorous	potassium
sodium	bilirubin (total and direct)	total protein	BUN	Uric acid
eGFR ⁴	HbA1c	β-2 microglobulin		
Coagulation (central laboratory)				
INR or PT	aPTT			
Thyroid function (central laboratory)				
TSH	free T4			
Urinalysis macroscopic ⁶ (local laboratory):				
pH	specific gravity	glucose	ketones	leukocytes
nitrites	protein	occult blood		
Urinalysis microscopic [optional] (local laboratory):				
RBC	WBC	bacteria	casts	epithelial cells
mucous threads	crystals			
Urinalysis or serum (local laboratory)				
β-HCG ⁵				
Immunoglobulins (central laboratory)				
IgG	IgA	IgM		
Other assessments (central laboratory)				
cytokines	complement	ADA/NAb	histamine	B-cell count
rituximab	PK (serum)	PK (CSF)		
Other assessments (local laboratory)				
Viral loads (HIV, HBV, HCV)	CD4+ T-cell counts			

β-HCG = beta human chorionic gonadotropin; ADA = anti-drug antibody; AST = aspartate aminotransferase; ALT = alanine aminotransferase; aPTT = Activated partial thromboplastin time; BUN = blood urea nitrogen; CPK = creatinine phosphokinase; CSF = cerebrospinal fluid; eGFR = Estimated glomerular filtration rate; freeT4 = Free thyroxin; GGT = gamma-glutamyl transferase; HbA1c = Glycated hemoglobin; HBV = hepatitis B virus; HCV = hepatitis C virus; HIV = human immunodeficiency virus; Ig = immunoglobulin; INR = International normalized ratio; LDH = Lactate Dehydrogenase; NAb = Neutralizing antibodies; PK = pharmacokinetics; PT = Prothrombin time; RBC = Red Blood Cell; TSH = Thyroid-stimulating hormone; WBC = white blood cell.

¹WBC with differential (including neutrophils, basophils, eosinophils, lymphocytes, monocytes) reported as percentage and absolute values

²Red cell indices (mean cell volume [MCV], mean corpuscular hemoglobin [MCH], mean corpuscular hemoglobin concentration [MCHC]) and distribution widths (red cell and platelet)

³If possible, the blood for chemistry assessments should be drawn after a subject has fasted for at least 2 hours, in order to facilitate a more reliable interpretation of the serum glucose result. The compliance with this recommendation (Yes / No) will be entered in the eCRF for every chemistry assessment.

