8.3 Clinical Laboratory Assessments

Laboratory assessments will be summarized by presenting descriptive statistics of raw data and change from baseline. Listings will include flags for values outside of the reference ranges, and clinical significance if a laboratory result is deemed abnormal.

The following tests will be performed by the central laboratory:

- Hematology
- Chemistry (with eGFR)
- HbA1c
- Coagulation (aPTT and either INR or PT)
- Thyroid function (TSH and FT4)
- Serum cytokines
- Histamine
- Complement
- Immunoglobulins
- B-cell count and immunophenotype (flow cytometry)

The following laboratory tests will be performed in the local laboratory at the site:

- Urinalysis (Dipstix)
- Pregnancy test (serum or urine)
- Serology for HIV, HBV and HCV (if applicable)

A shift table displaying baseline CTCAE grade to maximum post-baseline CTCAE grade will be presented for hematology and chemistry lab values.

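### The combined-liver-injury stopping rule in Table 7 (row 4) needs alkaline phosphatase and INR, which the protocol's scheduled tests do not supply when the rule has to be applied

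*Protocol*

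**What the plan says.** Table 7 in Protocol Section 5.4.5 gives dose actions by worst AST/ALT and worst bilirubin. Three rows matter here.

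- Row 1 covers isolated AST/ALT up to 5 × ULN or isolated bilirubin up to 1.5 × ULN. Its action is "No change in study drug", with monitoring.
- Row 2 includes bilirubin above 1.5 and up to 5.0 × ULN. Its action is "Temporarily or permanently (see next row) discontinue study drug", with resumption one dose level lower once values recover to Grade 1 or less, or to baseline.
- Row 4 is a permanent stop. The enzyme condition is AST/ALT above 3.0 × ULN "without findings of cholestasis defined as serum alkaline phosphatase" below 2 × ULN. The second condition is bilirubin above 2.0 × ULN or INR above 1.5.

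The text below the table calls these actions recommendations and adds that "the investigator is encouraged to contact the medical monitor to discuss alternative course of action".

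The chemistry panel in Appendix 1, Table 10 includes AST, ALT, GGT and "bilirubin (total and direct)", but not alkaline phosphatase. Chemistry is drawn at screening, "Before the MT-3724 infusion on D1, D8", on D15 of each cycle, and at EoT (Section 6.4.1). Coagulation is drawn at screening, "Before MT-3724 dose on D1 of cycle 3 and each odd cycle thereafter", and at EoT (Section 6.4.6; Table 3, footnote 6). Table 10 accepts INR or PT, and SAP Section 8.3 likewise lists "Coagulation (aPTT and either INR or PT)".

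**The concern.** A stopping rule can be applied only if its inputs are measured. Row 4 needs alkaline phosphatase in every case, and it needs INR whenever bilirubin is not above 2.0 × ULN. The protocol schedules the first test nowhere and the second too rarely to accompany most liver panels. Table 7 does not say how to read row 4 when alkaline phosphatase is missing.

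What is at stake is subject safety. A site that follows the schedule as written could leave a subject on full dose, or restart a held subject at a reduced dose, where the protocol's own rule points to a permanent stop.

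**Working it through.** There is no plan figure to reproduce. The check sets the inputs of row 4 against the panel and the visit schedule.

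**Panel content.** Table 10 lists chemistry in rows of 5, 5, 5, 5 and 3 entries: 5 + 5 + 5 + 5 + 3 = 23. Alkaline phosphatase is not one of them. The first four rows have every cell filled, and the abbreviation list under the table spells out ALT, AST, CPK, GGT and LDH but not alkaline phosphatase, so loss in text conversion is unlikely. No other part of the protocol or SAP names the analyte.

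**Timing, cycles 1–2.** Chemistry falls on D1, D8 and D15 of each 28-day cycle. Excluding the pre-dose C1D1 sample, the panels before cycle 3 fall on study days 8, 15, 29, 36 and 43, which is 5 panels, 2 of them in cycle 1. The first on-treatment coagulation draw is C3D1, day 2 × 28 + 1 = 57. Screening safety laboratories may be up to 28 days before C1D1, so by C3D1 the last scheduled coagulation result can be 28 + 56 = 84 days old, assuming no dose delays.

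**Timing, later cycles.** Taking cycles 1–6 as an illustration (the protocol sets no cycle limit), post-dose chemistry panels number 6 × 3 − 1 = 17. Coagulation coincides with two of them, C3D1 (day 57) and C5D1 (day 113). That leaves 17 − 2 = 15 panels, or 15/17 = 88%, without a same-day coagulation draw.

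**Effect on the action.** Take AST at 4 × ULN, without the symptoms that trigger row 5:

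| Bilirubin (× ULN) | Action readable from scheduled tests | When row 4 would apply | What the missing tests decide |
|---|---|---|---|
| ≤1.5 | Row 1: dosing unchanged | Alkaline phosphatase <2 × ULN and INR >1.5 | Whether dosing continues at all |
| >1.5 to 2.0 | Row 2: stop, may resume lower | Alkaline phosphatase <2 × ULN and INR >1.5 | Whether dosing may resume |
| >2.0 to 5.0 | Row 2: stop, may resume lower | Alkaline phosphatase <2 × ULN, whatever the INR | Whether dosing may resume |
| >5.0 | Row 6: permanent stop | Not needed | Nothing |

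Only the first line can leave a subject on drug. In the second and third lines the drug stops immediately under either row.

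**Overlap with the DLT criteria.** Appendix 4 counts AST/ALT above 3.0 × ULN with total bilirubin at or above 2.5 × ULN as potentially dose-limiting, without alkaline phosphatase or INR. In cycle 1 of Part 1, Section 5.4.1 then has MT-3724 discontinued unless the investigator's benefit-risk assessment supports continuing. Within that window, row 4 adds something only for bilirubin above 2.0 and below 2.5 × ULN, or for a raised INR with bilirubin at or below 2.0 × ULN. In Part 2 and in later cycles there is no such default.

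**The case against.** The strongest reply is that the gap is small in practice, and much of that reply stands.

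- Table 7 is advisory, applies to increases judged possibly drug-related, and works through medical-monitor consultation.
- Unscheduled tests are allowed. Section 5.4.1 recommends notifying the medical monitor within 24 hours of a qualifying event and doing diagnostic procedures if needed. Section 6.4 has an unexplained significant abnormality repeated and followed until it normalises or is explained. A careful investigator would probably order both tests. Still, none of these provisions names alkaline phosphatase or INR, and the local-laboratory provision in Section 6.4.1 covers chemistry and hematology, not coagulation.
- GGT and direct bilirubin are collected, so the panel is not blind to cholestasis. They do not, however, satisfy row 4's own definition.
- Row 1 is confined to isolated increases, so a raised INR arguably takes the subject out of it. That helps only if the INR has been measured.
- Accepting INR or PT is largely a reporting choice within one test, and little weight should rest on it.

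A reader might infer that subjects with raised enzymes and raised bilirubin would go on being dosed because alkaline phosphatase is missing. The documents do not support that: row 2 already stops the drug once bilirubin exceeds 1.5 × ULN, and it bars resumption until recovery, which leaves time to order the test.

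A reader might also take the 88% as a measure of risk. It describes the visit schedule over a chosen six cycles. Row 4 matters only when AST or ALT is above 3.0 × ULN.

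**Conclusion.** The point holds in a limited form. Row 4 cannot be applied from the scheduled tests, and no other text requires the missing ones. The material case is narrow: AST/ALT above 3.0 and up to 5.0 × ULN, bilirubin at or below 1.5 × ULN, and a raised INR that nobody has measured. Such a subject could remain on drug. Where bilirubin is above 1.5 and up to 5.0 × ULN, the missing tests affect only whether a reduced dose may be resumed.

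A reader might infer that the dose-finding result is compromised. It is not: the liver criteria in Appendix 4 use neither test, so DLT counting and the MTD rule are unaffected.

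The conclusion assumes that Table 10 as printed is the complete panel and that sites draw what is scheduled. The documents give no basis for estimating how many subjects would be affected. The correction is worth making because it is cheap and supplies the inputs to a rule that the protocol already contains.

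**What to change.** 1. Add alkaline phosphatase to the chemistry panel in Table 10.
2. In Section 6.4.6 and Table 3 footnote 6, require an INR whenever AST or ALT exceeds 3.0 × ULN, taken from the same sample or a local draw where possible and available before the next dose. Footnote 6 also serves the thyroid and HbA1c rows, so the addition should be worded for coagulation only.

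Leave all Table 7 thresholds as they are. A reader might want the bilirubin column rewritten to use direct bilirubin in Gilbert's syndrome, as inclusion criterion 10a does at entry. That would change the operative limits for those subjects and is a separate clinical decision. How to handle subjects on anticoagulants, or those enrolled with AST/ALT of 3–5 × ULN, likewise stays with the sponsor and medical monitor.

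The cost is one analyte on an existing draw and an occasional extra INR: at scheduled panels, at most 3 per 28-day cycle if the enzymes stay raised on D1, D8 and D15. A reflex INR after D15 of cycles 1–2 may need an unscheduled visit, because no MT-3724 infusion is normally due again until the next D1. LEN, however, continues daily to D21, up to 6 further doses (D16–D21), so waiting for the next infusion visit would be too late.
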